10.3.3 Study Completion/Termination

At study completion (Week 48/end of treatment visit [ETV]), the following assessments will be done:

- Patient-reported questionnaires: DLQI and EQ-5D-5L (should be completed prior to any other assessments are done)
- Review of concomitant medications/non-drug therapies
- AE monitoring
- sPGA, PASI, BSA evaluation
- Complete physical examination
- Vital signs (body temperature, pulse rate, blood pressure, respiratory rate, and measure body weight)
- 12-lead ECG
- PK and immunogenicity
- Clinical laboratory assessments (hematology and serum chemistry)
- Urinalysis
- Urine pregnancy test (female subjects of childbearing potential only)
- Injection site evaluation
- Study drug return

10.3.4 Safety Follow-up

At the safety follow-up visit (Visit 20; Safety Follow-up, Week 52 ± 2 weeks), the following assessments will be performed:

- Review of concomitant medications/non-drug therapies
- AE monitoring
- sPGA, PASI, BSA evaluation
- Brief physical examination
- Vital signs (body temperature, pulse rate, blood pressure, and respiratory rate and measure body weight)
- PK and immunogenicity

- Clinical laboratory assessments (hematology and serum chemistry)
- Urinalysis
- Urine pregnancy test (female subjects of childbearing potential only)

The safety follow-up visit is done by subjects who completed the study treatment as per protocol requirements and those who have withdrawn from the study early.

If the subject does not show up to the clinical visit, the site should try contacting the subject by phone for at least 8 weeks after the scheduled follow-up visit and obtain information regarding the occurrence of adverse events, treatments for psoriasis as well as other concomitant medications and pregnancy status. In case the subject is a female of childbearing potential, at Week 48 a urine dipstick pregnancy test should be provided.

Information collected after Week 52 visit will be collected only as source data and not included in the eCRF.

At the safety follow-up visit the investigator should consider the next therapy to prescribe to the subject off-study, in order to maintain clinical benefit.

10.4 Medications and Non-Drug Therapies

During the study, subjects are expected to be on concomitant medication(s) if they are being treated or receiving prophylaxis for any underlying medical conditions, provided the medications are not considered psoriasis therapies. Subjects may take allowed additional concomitant medication(s) as needed for medical management during this study. All medications taken 4 weeks prior to screening and concomitant medication use should be recorded in the appropriate eCRF. Exposure to all biologic medications at any time should be collected.

The following medications and non-drug therapies are **not** permitted during the course of the study:

- Medications:
 - Systemic TNF inhibitor therapy, or B-cell depleting therapy, including other investigational biosimilar TNF inhibitors or B-cell depleting therapies, or 2 or more non-TNF biologic therapies
 - Other biologic immunomodulating therapies such as ustekinumab or other licensed or investigational biologics within 24 weeks prior to baseline (Visit 2) and during the duration of the study. Prior exposure to more than one such biologic immunomodulating therapy not permitted

- Systemic treatment with licensed or investigational immunosuppressive or targeted agents such as, but not limited to, cyclosporine, tacrolimus, MTX, azathioprine, 6-mercaptopurine, or hydroxyurea within 8 weeks prior to baseline (Visit 2) and during the duration of the study; excepting apremilast, tofacitinib within 4 weeks prior to baseline and during the duration of the study
- Systemic and topical retinoid or Vitamin D analog therapy within 4 weeks prior to baseline and during the duration of the study. Up to 1000 IU/day average dose of Vitamin D therapy is permitted if stable dose for 4 weeks prior to screening and during the duration of the study
- Topical calcineurin inhibitors, such as pimecrolimus, within 4 weeks prior to baseline and during the duration of the study
- Topical or systemic corticosteroids for treatment of psoriasis within 4 weeks prior to baseline and during the duration of the study. Topical steroids of weak potency (World Health Organization group VII) will be permitted for use during the study, but must not be used within 24 hours of study visits. Systemic corticosteroids used within the last year prior to screening for conditions other than psoriasis are not permitted
- Topical treatments containing acetylsalicylic acid, if used for psoriasis
- Topical tar derivatives within 2 weeks prior to baseline and during the course of the study
- Phototherapy and photochemotherapy within 4 weeks prior to baseline and during the course of the study. Subjects should be advised to avoid tanning booths and excessive sun exposure, eg, sun bathing
- Shampoos, moisturizers, and emollients that do not contain salicylic acid, tar, corticosteroids, and vitamin D analogs are allowed but must not be used in the 12 hours prior to study visits
- All other prior non-psoriasis concomitant treatments must be on a stable dose for at least 4 weeks prior to baseline
- Injectable anti-infective therapy within 30 days, or oral infective therapies within 14 days of baseline
- Live/attenuated vaccination within 6 weeks prior to baseline and during the duration of the study is not allowed

A subject who has taken any of these medications or received any of these non-drug therapies will be discontinued.

10.5 Subject Diary

A paper subject diary will be provided to each subject at each visit to record the following information, as applicable according to [Table 1](#):

1. Time, date, and location of IP administration; including whether the full dose was administered and, if not, why the full dose was not administered (eg, device malfunction)
2. IP administrator (self or caregiver)
3. AEs, including injection site reactions

Subjects and/or their legally authorized representatives will be trained on use of the diary. The diary will be provided in paper format and the subject should bring the completed diary to the site at each visit. The investigator will review the diary for completeness, request missing information periodically and in a timely manner, photocopy the applicable pages, store them in the source documents until such time when the original subject diary is collected. Untoward events recorded in the diary will be reported as AEs according to the investigator's discretion and clinical judgment.

During the treatment period, at Week 25, the subject diary may be collected and a new diary provided to the subject and retrieved at Week 48.

The subject diary will serve as a source record and remain at the study site once collected. Entries in the subject diary will be transferred into the eCRF. Any entry in the eCRF that does not correspond with an entry in the subject diary will be explained by the investigator in source documentation.

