6. BACKGROUND INFORMATION

6.1 Description of Investigational Product

M923 is a proposed adalimumab biosimilar. HUMIRA® (hereafter referred to as Humira) is the United States (US)-licensed reference product and contains adalimumab as the active substance. Adalimumab is a recombinant human immunoglobulin G subclass 1 (IgG1) monoclonal antibody specific for human tumor necrosis factor-alpha (TNF)-alpha. Unlike etanercept, adalimumab does not bind to TNF-beta.

Humira is licensed for use in the US and European Union (EU); Humira approved in the EU, which is the Reference Protein Product (EU RPP) in this study, is not approved for use in the US and hence is considered an investigational new drug. Hereafter, Humira licensed in the US is referred to as the US Reference Product (US RP), and the non-US-approved comparator (EU-approved Humira) is referred to as the EU RPP.

M923 injection is a preservative-free, sterile solution for subcutaneous (SC) administration and is provided as single-use, 1.0 mL prefilled glass syringes that deliver 40 mg (0.8 mL) of M923. M923 is produced by recombinant deoxyribonucleic acid technology in a Chinese hamster ovary mammalian cell expression system and is purified by a process that includes specific viral inactivation and removal steps. The amino acid sequences of M923 and adalimumab are identical. The M923 formulation has a different buffer composition than the EU RPP and the US RP; however, the solution characteristics (pH, osmolality) of M923 are found to be within pre-specified acceptance criteria to those of the EU RPP and are expected to exhibit corresponding physiologic effects. There are no new components in the M923 buffer.

The M923 dose selected for this study is based on the recommended dose of US RP and EU RPP for adult patients with active chronic plaque psoriasis, ie, an initial dose of 80 mg administered SC, followed by 40 mg SC given every other week starting 1 week after the initial dose.⁴ The safety profile of M923 is anticipated to correspond to the EU RPP. Investigators should carefully monitor for all adverse events (AEs), including AEs not described as associated with the EU RPP. The pharmacokinetic (PK) profile of M923 is currently being evaluated in an ongoing PK Phase 1 clinical study; results are not yet available.

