8.7.3 Description of Treatment

Subjects will be administered 80 mg of M923 or EU RPP at Week 0 and then 40 mg every 2 weeks (Q2W) starting at Week 1 of the study. Self-injections should occur on the same day (\pm 3 days) each treatment week according to a predetermined randomization schedule with 2 arms indicated as follows:

- Arm A: M923 from Weeks 0 to 48 (n = 258 subjects)
- Arm B: EU RPP from Weeks 0 to 16 (last dose at Week 15); then randomized again at Week 16 into Arms B1 and B2:
 - Arm B1: Continues EU RPP from Weeks 17 through 48 (last dose at Week 47; n = up to 129 subjects)
 - Arm B2: Transition to M923 at Week 17; then to EU RPP at Week 25; and to M923 at Week 37 (last dose at Week 47; n = up to 129 subjects)

At Weeks 0, 1, 17, 19, 21, 25, 27, 37, and 39, injections will be administered in the clinic after all required assessments and blood sample collections have been completed.

All other injections will be administered by the subjects or caregiver at home (but after assessments completed if a planned injection date coincides with a planned visit date [Weeks 29, 33, 41, and 45]). When injection occurs in the clinic, subjects should be observed for 2 hours in the clinic post-injection at Weeks 0, 1, 17, 25, and 37; at Weeks 19, 21, 27, and 39, subjects should be observed for 30 minutes after injection.

At any time during the study, any of the IPs may be interrupted or discontinued at the discretion of the investigator based on his/her evaluation of the subject's condition or safety. No dose modification is permitted for this study.

When injection occurs in the clinic, the investigator or a qualified designee will evaluate the current injection sites 30 minutes (\pm 10 minutes) after study drug administration in the clinic at Weeks 0, 1, 17, 19, 21, 25, 27, 37, and 39.

They should also evaluate immediately prior injection site at each subsequent visit as applicable ([Section 12.10](#)). For injections given at home, injection site reactions will be recorded in the subject diary ([Section 10.5](#)). There will be no injection at Week 48 (Visit 19), but injection site evaluation for previous injections will occur.

Any injection site reactions, regardless of causality, will be recorded on the AE electronic case report form (eCRF). Any concomitant medications, including those used to treat AE(s), will be recorded on the appropriate eCRF.

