12. ASSESSMENT OF SAFETY

12.1 Adverse Events

12.1.1 Definitions

An AE is defined as any untoward medical occurrence in a subject administered an IP that does not necessarily have a causal relationship with the treatment. An AE can therefore be any unfavorable and unintended sign (eg, an abnormal laboratory finding), symptom (eg, rash, pain, discomfort, fever, dizziness, etc.), disease (eg, peritonitis, bacteremia, etc.), or outcome of death temporally associated with the use of an IP, whether or not considered causally related to the IP.

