12.10 Injection Site Evaluations

The current and prior site of SC injection of the study drug to the lower abdomen or thigh will be assessed for immediate local reactions 30 minutes (\pm 10 minutes) after injection. In addition, there will be an observation period for a minimum of 2 hours post injection after administration of M923 or EU RPP onsite at Weeks 0, 1, 17, 25, and 37. For injections given at home, injection site reactions will be recorded in the subject diary as described in [Section 10.5](#).

Injection site evaluations will be made by clinical staff or by the subject or caregiver, as described below; if an injection site reaction is observed, a physician will characterize and document the reaction as an AE. Injection sites will continue to be reviewed at the time points indicated in [Table 1](#), or until the AE is resolved.

Injection sites will be monitored for pain, tenderness, erythema, and swelling. Each injection site reaction will be categorized using the intensity grading scheme presented in [Table 3](#); the intensity of each resulting AE will be categorized as described in [Section 12.1.2.1](#) (eg, a moderate intensity injection site reaction may be recorded as a mild AE if considered appropriate according to the investigator's judgment, based on the AE grading schemes presented in [Section 12.1.2.1](#)).

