Tuberculosis (TB)	QuantiFERON®-TB Gold test	T-SPOT
Serum/urine pregnancy test	Beta human chorionic gonadotropin	Follicle-stimulating hormone

IgG = immunoglobulin G; IgM = immunoglobulin M.

Table 3
Injection Site Reaction Grading Scheme

Reaction	Intensity Grading				
	Absent (0)	Mild ^a (1)	Moderate ^a (2)	Severe ^a (3)	Potentially Life-threatening (4)
Pain	Absent	Does not interfere with activity	Repeated use of non-narcotic pain reliever >24 hours or interferes with activity	Any use of narcotic pain reliever or prevents daily activity	Hospital visit (A and E) or hospitalization
Tenderness	Absent	Mild discomfort to touch	Discomfort with movement	Significant discomfort at rest	A and E visit or hospitalization
Erythema/ redness	Absent	2.5 to 5.0 cm	5.1 to 10.0 cm	>10.0 cm	Necrosis or exfoliative dermatitis
Induration/ swelling	Absent	2.5 to 5.0 cm and does not interfere with activity	5.1 to 10.0 cm or interferes with activity	>10.0 cm or prevents daily activity	Necrosis
Other ^b	Absent	Present			

A and E = accident and emergency department; AE = adverse event.

^a Measurements refer to the reaction at the greatest single diameter. Measurements of less than 2.5 cm diameter for erythema or induration may be captured as mild per investigator discretion.

^b Any other reactions such as bruising, itching or ulceration will be recorded as absent or present and will be recorded as AEs; AEs will be categorized according to the investigator's judgment, using the guidance presented in [Section 12.1.2](#)

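### Protocol Section 10.5 makes AE reporting of diary events discretionary, against the rules that every injection site reaction is recorded as an AE, and the diary is the named record for 16 of 25 dosing occasions

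*Protocol*

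**What the plan says.** Protocol Section 10.5 lists what the subject writes in the diary. One item is "AEs, including injection site reactions". The same section then says: "Untoward events recorded in the diary will be reported as AEs according to the investigator's discretion and clinical judgment". Further on it adds that diary entries are carried over to the eCRF, without naming the AE page.

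Four other places in the protocol treat recording as mandatory:

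- Section 8.7.3: "Any injection site reactions, regardless of causality, will be recorded on the AE electronic case report form (eCRF".
- Section 12.10, in the sentence that has evaluations made by clinic staff or by the subject or caregiver: "if an injection site reaction is observed, a physician will characterize and document the reaction as an AE".
- Table 3 footnote b (Section 20.2): "Any other reactions such as bruising, itching or ulceration will be recorded as absent or present and will be recorded as AEs".
- Section 12.1.1: "An AE is defined as any untoward medical occurrence in a subject administered an IP". Section 12.1.2 then requires each treatment-emergent AE to be described on the AE eCRF.

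For home injections, Sections 8.7.3 and 12.10 and Table 1 footnote p all name the diary as the place where reactions are recorded. Injection site reactions are part of a secondary safety outcome (Protocol 8.4.2.2, SAP 3.2). SAP 8.1 tabulates them as TEAEs, and SAP 10 examines them against ADA status.

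**The concern.** Section 10.5 gives the investigator discretion over entries that it already calls untoward. Under Section 12.1.1 such an event after dosing is an AE by definition, and an injection site reaction is an AE under three further rules. Elsewhere the protocol leaves only grading to judgment: the AE intensity in Section 12.10 and lesions under 2.5 cm in Table 3 footnote a. No sentence ranks Section 10.5 below the specific rules, so two sites can follow the protocol in good faith and record the same home reaction differently.

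At stake is how completely a named tolerability outcome is captured. Local reactions are one place where a product difference could appear, because "The M923 formulation has a different buffer composition than the EU RPP and the US RP". Section 6.1 also says that the buffer has no new components and that pH and osmolality met pre-specified criteria, so this is a reason to measure the outcome well and not evidence of a difference. If home reactions are under-recorded in both arms, an absolute difference shrinks and the products look more alike than they are.

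**Working it through.** **1. Dosing occasions.** The plan prints no total, so I count from Protocol 8.7.3 and Table 1 footnote n.

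- Clinic: Weeks 0, 1, 17, 19, 21, 25, 27, 37, 39 = 9
- Home, between visits: Weeks 3, 5, 7, 9, 11, 13, 15, 23, 31, 35, 43, 47 = 12
- Home, on a visit day after the assessments: Weeks 29, 33, 41, 45 = 4

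The total is 9 + 12 + 4 = 25, which is Week 0 plus the 24 odd weeks from 1 to 47. The SAP 6.6 expected-dose formulas agree: 48/2 + 1 = 25 at Week 48, and (47 + 1)/2 + 1 = 25 at Week 47. Home doses are 12 + 4 = 16, and 16/25 = 64%. Up to Week 15 there are 9 occasions, 7 of them at home (Weeks 3 to 15), and 7/9 = 78%.

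**2. Do other provisions close the gap?**

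- *Transfer of diary entries (10.5).* The AE page is not named, while the SAP tables are TEAE tables. The sentence that follows asks for an explanation when an eCRF entry has no matching diary entry. It does not cover a diary entry that is missing from the AE page.
- *Check of the prior site (8.7.3, Table 1 footnote p).* This covers only the immediately prior site, where applicable. With doses and visits at their nominal weeks, the sites from Weeks 5, 9, 13, 29, 33, 41 and 45 are never the immediately prior site at a visit, because another dose comes in between. That is 7 of 16 home doses. A short-lived reaction may also have resolved by the visit.
- *AE monitoring at visits (10.3.2).* This is a real second route, but it does not settle whether a reaction already in the diary must be entered.

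**3. Possible loss.** Let f be the share of home reactions omitted and h the home share of occasions. If reactions are equally likely at each occasion, the share of records lost is f × h. The documents give no value for f, so I show a range.

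| f (assumed) | All weeks, h = 16/25 | Weeks 0 to 15, h = 7/9 |
|---|---|---|
| 10% | 6.4% | 7.8% |
| 25% | 16.0% | 19.4% |
| 50% | 32.0% | 38.9% |

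With the same f in both arms, each arm's expected count is multiplied by (1 − f × h). An absolute difference in counts shrinks by that factor, and a ratio of counts is unchanged. Subject-level incidence is affected less, because a subject with several reactions still counts if one is recorded.

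**4. Arms and periods.** Arms A, B1 and B2 have identical clinic and home weeks, so h is the same for every arm within a period. Across periods it is not. With each switch-week dose placed in the new period, the home share is 7/9, 1/4, 4/6 and 4/6 for Periods 1 to 4. At f = 50%, capture is 1 − 0.5 × 7/9 = 61.1% in Period 1 and 1 − 0.5 × 1/4 = 87.5% in Period 2, a ratio of 1.43. At f = 10% the figures are 92.2% and 97.5%, a ratio of 1.06. A crude rise in recorded reactions per dose from Period 1 to Period 2 could therefore be partly an artefact.

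**The case against.** The strongest reply is that the mandatory rules already reach home reactions. Section 12.10 includes observation by the subject or caregiver in the sentence that requires documentation as an AE, and Section 10.3.2 sends home evaluations to Section 12.10. Section 8.7.3 states its rule directly after describing home diary recording. On this view Section 10.5 is a general sentence that yields to the specific ones, and some judgment over lay diary notes is needed anyway, for example under Section 12.1.1.4 on unchanged preexisting disease.

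Much of this stands. A reader might infer that the protocol lets sites drop home reactions while requiring them for clinic doses. It does not: the documents draw no home and clinic line in the duty to record. What remains is that Section 10.5 says something different, gives no cross-reference and names no order of precedence.

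A reader might also infer that the comparison of the transition arm with continuous EU RPP is biased. The documents do not support that. Protocol 13.4.4.2 and SAP 8.1 compare arms within each period, and the arms share their dosing locations. Nor could a safety equivalence test be passed falsely, since SAP Section 8 plans no formal testing of safety data.

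**Conclusion.** The contradiction is real and sits in the current text: discretion in Section 10.5 against mandatory recording in Sections 8.7.3, 12.10 and 12.1.1 and in Table 3 footnote b. It is an inconsistency of wording with a practical consequence, because the diary is the named record for 64% of dosing occasions and for 78% of those in the parallel comparison up to Week 15.

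Within a period the consequence is under-capture that varies by site, with less sensitivity to an absolute difference and no direction favouring either product. Only crude comparisons across periods could be distorted, because the home share differs. The amount is unknown. The losses of 6% to 32% overall (8% to 39% up to Week 15) are scenarios, not estimates. They rest on an assumed omission rate, equal reaction probability at each occasion and equal omission in both arms, which is plausible under blinding. The point is worth correcting but does not threaten the primary analysis.

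**What to change.** Reconcile Section 10.5 with Sections 8.7.3, 12.10 and 12.1.1 by replacing the discretion sentence with text to this effect:

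- Every injection site reaction recorded in the diary is entered on the AE eCRF and graded by Protocol Table 3.
- Every other diary entry is entered as an AE if it meets Section 12.1.1, subject to Section 12.1.1.4 on preexisting disease.
- Investigator judgment covers whether an entry is an untoward medical occurrence, and its diagnosis, severity and causality. The reason for any non-entry is written in source.

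Send sites a short reminder, and reconcile the diary pages already held against the AE eCRF before database lock. Section 10.5 already has diaries reviewed at visits, photocopied and kept as source, so the material is available. The cost is a few more mild AE entries and a modest reconciliation effort.
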